## Summary of the Clinical Trial Protocol and Statistical Plan

Name of Sponsor/Company:	AiCuris Anti-infective Cures GmbH	
Title of the trial: A randomized, double-blind, multi-center, three arm (pritelivir, placebo and Zovirax ® ) parallel group, comparative trial to assess the efficacy and safety of pritelivir 5% w/w ointment for the treatment of recurrent herpes labialis in adults – LipP 1		
Trial center(s): 10 to 14 investigational sites in the US		
Planned study period (years): First Subject First Visit: 4 th quarter 2016 Last Subject Last Visit: 3 rd quarter 2017	Phase of development: 2	
Objectives: To assess the efficacy, tolerability and safety of pritelivir 5% w/w ointment applied 5 times daily for 4 days for the treatment of recurrent herpes labialis (rHL) in adults		
Trial design: This is a randomized, double-blind, multi-center, three arm parallel group, comparative trial to assess the safety and efficacy, ie, proportion of subjects with non-ulcerative lesions, in adult subjects with rHL treated with pritelivir 5% w/w ointment. The statistical superiority will be tested against placebo and a descriptive comparison with Zovirax ® Cream will be made. The start of treatment with trial medication will be initiated by the subject within one hour of noticing the first sign or symptom (eg, prodrome) of a recurrence of herpes labialis (HL). Trial medication will be applied to the affected area 5 times daily for 4 days.		
Number of subjects (planned): approx. 360 subjects should be enrolled resulting in at least 71 subjects dosed in each treatment arm.		

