
Diagnosis and main criteria for inclusion:
 
 
1. Healthy men and women of any ethnic group aged <math>\geq 18</math> years ;
 
2. Subjects should have experienced <math>\geq 4</math> recurrences of HL in the previous 12-month period;
 
3. Subjects should have experienced prodromal symptoms in at least 50% of rHL episodes and should have developed ulcerative lesions that have progressed through vesicle, ulcer, and crust stages in at least 50% of the episodes;
 
4. Willingness not to use any topical application (such as cosmetics, lip balm, sunscreens etc.) other than the trial medication in the area of lesion development from start of prodromal symptoms to healing;
 
5. Willingness not to use any systemic and topical anti-HSV agent during the trial participation including prescription and over-the-counter products,
 
6. Willingness not to use any systemic, anti-inflammatory or analgesic agents from start of prodromal symptoms to healing;
 
7. Willingness to refrain from mechanical disruption (ie, scrubbing, lancing, shaving) of the prodromal area or lesion after start of treatment with trial medication until end of the trial participation;
 
8. Women of child bearing potential and males must use adequate contraception;
 
9. Subject must give written informed consent.
 
10. Subjects with current lesion may be enrolled, but must not to treat the lesion present at randomization with the trial medication; they should be instructed to wait for the next subsequent lesion.
 
		

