**Criteria for evaluation:**

**Efficacy:**

[figure not shown]
Primary endpoint:

- The percentage of subjects with non-ulcerative lesions in each treatment group.

Secondary endpoints:

- Duration of lesion episode (DOE), defined as time from treatment initiation to the healing of the primary lesion (loss of crust) for subjects who experienced a vesicular lesion. For subjects whose primary lesions were not vesicular in nature, DOE is the time from the treatment initiation to the return to normal skin or to the cessation of symptoms, whichever occurs last;
- Pain rate, defined as number of days with pain at lesion site relative to the total number of days with analyzable pain through daily subject self-assessment;

- Subject-assessed duration of lesion pain, defined as the time from first dose of trial medication until pain is no longer reported by the subject (date and time);
- Subject-assessed severity of lesion pain defined as the average daily NUMERICAL RATING SCALE (NRS) pain score using a single-dimensional scale assessing pain intensity at lesion site, 11 intensities [no pain (0) to worst pain imaginable (10)];

- Maximum lesion area (length x width) for ulcerative lesions during the vesicular, ulcerative and hard crust stages;
- Cumulative lesion area (sum of daily maximum lesion areas);
- Duration of lesion tenderness (unpleasantness upon touching the affected area).

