**Methodology:**

**Efficacy measurements:**

After self-initiation of treatment with trial medication subjects will be assessed daily for the following parameters by the Investigator until healing:

1. Lesion stage:
  - prodrome (symptoms including itching, pain, tingling, but no physical evidence of disease by inspection or by palpation in the application area),
  - erythema
  - papule (any elevation of skin without fluid in the application area)/edema,
  - vesicle (blister, fluid filled or collapsed, in the application area),
  - ulcer/soft crust,
  - hard crust,
  - residual abnormalities (residual erythema/scaling),
  - normal appearing skin.

2. Maximum lesion area (length x width) in mm^2

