**Statistical methods:**

**Sample size calculation:**

The primary endpoint will be the percentage of subjects with non-ulcerative lesions in each treatment group.

The percentage of subjects with non-ulcerative lesions if left untreated with HL is estimated as 26%. The percentage of subjects with non-ulcerative lesions is assumed to be 50% when applying pritelivir 5% w/w ointment as compared to placebo. The following table shows the total number of subjects with recurrences needed to show superiority of pritelivir compared with placebo with 80% power and assuming a type I error rate of 5%.

Proportion of subjects with non-ulcerative lesions:		Total number of evaluable recurrences needed 1:1:1 randomization			Total evaluable recurrences needed	Total number of subjects needed (including 40% who do not develop a recurrence)
Placebo	Pritelivir	Pritelivir	Placebo	Zovirax®		
26%	50%	71	71	71	213	360

It is assumed that 71 recurrences in each arm are sufficient to allow for a descriptive comparison of pritelivir with Zovirax®.

In order to obtain 213 evaluable HL recurrences, 360 subjects need to be randomized in a 1:1:1 randomization scheme to cover the rate of approx. 40% of subjects which do not develop a recurrence or drop out.

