**Secondary efficacy analyses**

The secondary efficacy analyses will be performed in the ITT and the PPS.

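### Maximum lesion area is defined only for ulcerative lesions, a subset that treatment is expected to change, so its between-arm difference should be reported descriptively

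*Combined protocol and SAP*

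**What the plan says.** All places are in the combined protocol and SAP.

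- **Criteria for evaluation, Efficacy.** The primary endpoint is the percentage of subjects with non-ulcerative lesions, by arm. The secondary list of seven includes "Maximum lesion area (length x width) for ulcerative lesions during the vesicular, ulcerative and hard crust stages". The next area endpoint, cumulative lesion area, sums the daily maximum areas and is not restricted by lesion type.
- **Secondary efficacy analyses.** The whole section is one sentence: "The secondary efficacy analyses will be performed in the ITT and the PPS". The ITT set (Primary efficacy analysis) takes in every randomized subject with at least one application and one later lesion assessment, so it includes subjects whose lesions never ulcerate. No value is given for them on maximum area.
- **Trial design.** "The statistical superiority will be tested against placebo and a descriptive comparison with Zovirax" Cream is planned. Only the Zovirax comparison is called descriptive.
- **Sample size calculation.** "The percentage of subjects with non-ulcerative lesions if left untreated with HL is estimated as 26" per cent, and "The percentage of subjects with non-ulcerative lesions is assumed to be 50% when applying pritelivir 5% w/w ointment as compared to placebo".
- **Methodology, Efficacy measurements.** "subjects will be assessed daily for the following parameters by the Investigator until healing". Both lesion stage and maximum area are on that list, with no limit by lesion type.

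**The concern.** Ulceration happens after randomization, and it is the outcome the drug is meant to prevent. Restricting an endpoint to subjects who ulcerate compares two groups selected differently by treatment: on placebo, everyone who would ulcerate without active drug; on pritelivir, only those in whom the drug failed to prevent it. If the lesions that the drug aborts would have been smaller or larger than the rest, the subset averages differ between arms even when the drug has no effect on the size of any lesion that does ulcerate.

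The interpretation is at stake in both directions. A drug that mainly aborts small lesions could appear to enlarge lesions. A drug that mainly aborts large ones could appear to shrink those that remain. Nothing in the plan limits what may be concluded from such a difference.

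**Working it through.** **1. The plan's own figure.** Inputs from Sample size calculation: 26% vs 50% non-ulcerative, 80% power, 5% type I error (taken as two-sided, which the text does not state). With mean proportion 0.38:

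n = [1.96 × √(2 × 0.38 × 0.62) + 0.842 × √(0.26 × 0.74 + 0.50 × 0.50)]² / 0.24² = 63.0

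This rounds up to 64. With the continuity correction, n = (63.0/4) × [1 + √(1 + 4/(63.0 × 0.24))]² = 71.1, which is 72 rounded up; the plan states 71. The total reproduces as 213/0.60 = 355, against 360 stated. The planning rates can therefore be used as they stand.

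**2. Who has a maximum area.** If *ulcerative* means the same in both endpoints:

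- Placebo: (1 − 0.26) × 71 = 52.5 contribute, 18.5 do not.
- Pritelivir: (1 − 0.50) × 71 = 35.5 contribute, 35.5 do not.
- Ratio of contributors: 35.5/52.5 = 0.68.

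**3. What selection alone could do.** The documents give no area distribution, so everything in this step is assumed. Areas are lognormal with CV 0.6 to 1.0. The drug aborts k = 24/74 = 0.324 of would-be ulcerative lesions and has no other effect on area. A two-sided 5% t test on log area is applied to the ulcerative subset (the plan names no test). With u the size rank from 0 to 1, the abort probability is 1 if u < k and 0 otherwise (strict), 2k(1 − u) (full slope), k[1 + 0.5(1 − 2u)] (half slope) or k (unrelated), with mirror images when larger lesions are aborted. Results from 10,000 simulated trials per scenario and CV, 71 per arm:

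| Lesions aborted | False significance | Subset mean ratio, pritelivir/placebo |
|---|---|---|
| Strictly the smallest | 79.3–79.9% | 1.25–1.33 |
| Smaller more often, full slope | 22.9–23.5% | 1.15–1.21 |
| Smaller more often, half slope | 9.5% | 1.07–1.11 |
| Unrelated to size | 4.8–5.4% | 1.00 |
| Larger more often, half slope | 9.4–9.7% | 0.89–0.93 |
| Larger more often, full slope | 23.6–24.3% | 0.79–0.85 |
| Strictly the largest | 79.5–79.7% | 0.52–0.68 |

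Hand check of the first row: the ratio is Φ(σ − c)/(1 − k), with σ² = ln(1 + CV²) and c = Φ⁻¹(0.324) = −0.456. At CV 0.6, σ = 0.555 and the ratio is 0.844/0.676 = 1.25. At CV 1.0, σ = 0.833 and it is 0.901/0.676 = 1.33.

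**4. A different model.** Let latent severity be N(0,1), with only the most severe 74% (placebo) or 50% (pritelivir) ulcerating, and let ρ be the assumed correlation of severity with area. The mean severity of the top fraction p is φ(c)/p, which is 0.438 at p = 0.74 and 0.798 at p = 0.50, so the spurious difference is ρ × 0.36 SD. That is 0.11, 0.18, 0.25 and 0.36 SD at ρ = 0.3, 0.5, 0.7 and 1, and a nominal 5% test rejects in about 8%, 15%, 28% and 72% of trials. At ρ = 0 there is no bias; with negative ρ the sign reverses.

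Both models show the same thing: the bias runs from nil to large, and its sign depends on which lesions are aborted, which the documents do not say.

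**The case against.** The strongest reply is that the plan never promises a test or a claim on this endpoint. The text is a summary, and no test is named for any secondary endpoint or for the primary one. Trial design equates efficacy with the proportion of non-ulcerative lesions, and the sample size section ties superiority and the 5% error rate to that endpoint. This stands. A reader might infer from the superiority sentence that a confirmatory test of maximum area is planned; the documents do not support that. What remains is that this is a listed efficacy endpoint, to be analysed in a set where many subjects have no value, with no limit on its interpretation.

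A reader might also infer that the documents contradict themselves on what *ulcerative* means, because the area window includes the vesicular stage while the stage list gives "vesicle (blister, fluid filled or collapsed, in the application area") separately from ulcer/soft crust. They do not. The inclusion criteria say that subjects "should have developed ulcerative lesions that have progressed through vesicle, ulcer, and crust stages in at least 50% of the episodes", so measuring such a lesion while it is still a vesicle is consistent. Whether a lesion that stops at vesicle counts is not spelled out, but that is a wording request.

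It is also fair that the restriction is openly stated, that an unrestricted area endpoint already exists, and that the simulated figures are not evidence about this trial. The 80% needs abortion to be determined perfectly by size.

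**Conclusion.** The point holds as a limit on interpretation, at minor severity. Maximum area among ulcerative lesions conditions on a post-randomization outcome that the plan itself assumes treatment will move from 74% to 50%. A pritelivir–placebo difference in that subset, favourable or adverse, cannot be read as an effect on lesion size.

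This rests on two conditions: that *ulcerative* has the same meaning in the primary and secondary endpoints (needed for exact complementarity and for the 52.5 and 35.5), and that treatment does change who ulcerates. The rejection rates and mean ratios rest on assumed models and only illustrate the range.

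A reader might go further and infer that the endpoint will be biased, or biased against pritelivir. The documents do not support either, since they do not say whether aborted lesions would have been small or large. One of seven secondary endpoints is affected; the primary analysis and the sample size are not.

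**What to change.** State in the SAP that maximum area among ulcerative lesions is a descriptive summary by arm, shown with the number of subjects contributing in each arm, and that no treatment effect on lesion size will be claimed from it. Base any between-arm inference on lesion area on an endpoint defined for all ITT subjects; the planned cumulative lesion area, which carries no restriction, is the obvious candidate.

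The cost is wording only, because stage and area are already assessed daily. The price is that there will be no inferential statement about maximum area given ulceration, and that cumulative area mixes size with duration.

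An all-ITT test of maximum area that scores non-ulcerative subjects 0 is optional, not required. It is a different estimand, partly repeats the primary endpoint and does not isolate size given ulceration. Under the assumptions of step 3 of the working, a rank test with every non-ulcerative subject at 0 has power of about 25% if the smallest lesions are aborted first, 73% if abortion is unrelated to size and 98% if the largest are aborted first, against about 84% for an uncorrected chi-square test of the primary endpoint.

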**Safety:**

- An overall summary of adverse events (AEs) will be provided including the number and percentage of subjects with any AE, treatment emergent AE (TEAE), related TEAE, serious AE, severe AE, and TEAE leading to early termination;
- TEAEs by system organ class (SOC), preferred term (PT), and treatment group. Summarization by maximum severity will also be presented;
- Safety laboratory parameters;
- Safety signals such as hematological changes, lymphadenopathy, CRP increase, cutaneous adverse events and changes in (a)PTT;
- Vital signs (systolic and diastolic blood pressure, pulse rate) by visit and treatment group;
- Standard 12-lead electrocardiogram (ECG) by visit and treatment group;
- Physical examination by visit and treatment group.

**Compliance:**

- The percentage compliance will be calculated as the number of doses applied documented in the diary divided by 20 times 100.

**Pharmacokinetics:**

- $C_{max}$ ,  $T_{max}$ , AUC, if feasible

**Methodology:**

**Efficacy measurements:**

After self-initiation of treatment with trial medication subjects will be assessed daily for the following parameters by the Investigator until healing:

1. Lesion stage:
  - prodrome (symptoms including itching, pain, tingling, but no physical evidence of disease by inspection or by palpation in the application area),
  - erythema
  - papule (any elevation of skin without fluid in the application area)/edema,
  - vesicle (blister, fluid filled or collapsed, in the application area),
  - ulcer/soft crust,
  - hard crust,
  - residual abnormalities (residual erythema/scaling),
  - normal appearing skin.

2. Maximum lesion area (length x width) in mm^2

**Subject diary documentation:**

Subjects will document the following in their diary:

1. Time of each application of trial treatment,
2. Pain intensity, changes in pain intensity, and cessation of pain at each application of trial treatment (at the first and last daily application as a minimum),
3. Pain intensity, changes in pain intensity, and cessation of pain in the morning and evening on days after stop of application of trial treatment until pain disappeared,
4. Lesion stage at each application of trial treatment,
5. Lesion stage in the morning and evening on days after stop of application of trial treatment until lesion healing,
6. Lesion tenderness at each application of trial treatment, and,
7. Lesion tenderness in the morning and evening on days after stop of application of trial treatment until lesion tenderness disappeared.

Subject diaries will be reviewed by the investigational site staff at each visit.

**Safety measurements:**

The following safety measures will be performed at screening and at Visit 5 (Day 5/6) and at the End of Trial Visit (Day 12±1) after initiation of treatment:

1. Safety laboratory parameters, ie, serum chemistry, hematology, coagulation and urinalysis
2. Vital signs, ie, systolic and diastolic blood pressure, pulse rate
3. Standard 12-lead electrocardiogram (ECG) according to Einthoven, Goldberger and Wilson
4. Physical examination including the assessment of the skin, head, eyes, ears, nose, neck, lymph nodes, throat, and extremities, and the following body systems: musculoskeletal, cardiovascular, respiratory, gastrointestinal and neurological.

Any other clinically relevant findings will be recorded.

**Blood sampling for pharmacokinetics:**

Blood sampling for pharmacokinetic analysis (one per day, in total seven samples) will be performed at randomization, daily at Visit 1 to Visit 5, and at the End of Trial Visit (Day 12±1).

The time of PK blood sampling will be documented.

**Statistical methods:**

**Sample size calculation:**

The primary endpoint will be the percentage of subjects with non-ulcerative lesions in each treatment group.

The percentage of subjects with non-ulcerative lesions if left untreated with HL is estimated as 26%. The percentage of subjects with non-ulcerative lesions is assumed to be 50% when applying pritelivir 5% w/w ointment as compared to placebo. The following table shows the total number of subjects with recurrences needed to show superiority of pritelivir compared with placebo with 80% power and assuming a type I error rate of 5%.

Proportion of subjects with non-ulcerative lesions:		Total number of evaluable recurrences needed 1:1:1 randomization			Total evaluable recurrences needed	Total number of subjects needed (including 40% who do not develop a recurrence)
Placebo	Pritelivir	Pritelivir	Placebo	Zovirax®		
26%	50%	71	71	71	213	360

It is assumed that 71 recurrences in each arm are sufficient to allow for a descriptive comparison of pritelivir with Zovirax®.

In order to obtain 213 evaluable HL recurrences, 360 subjects need to be randomized in a 1:1:1 randomization scheme to cover the rate of approx. 40% of subjects which do not develop a recurrence or drop out.

**Primary efficacy analysis:**

The primary efficacy analysis will be performed in the ITT (Intend to Treat Set) and the PPS (Per-Protocol Set).

ITT includes the results from all randomized subjects who applied the trial medication at least once and had at least one lesion status assessment done/reported after start of treatment.

PPS is a subset of the ITT excluding subjects with major protocol violations.

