**Safety**

All safety and tolerability parameters will be listed. All safety analyses will be performed in the Safety Set (= all randomized subjects who applied at least one dose of trial medication).

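### Does running the primary superiority analysis in both the ITT and the PPS leave the trial without a deciding result?

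*Combined protocol and SAP*

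**What the plan says.** The document is headed "Summary of the Clinical Trial Protocol and Statistical Plan". Under Trial design it plans one inferential comparison: "The statistical superiority will be tested against placebo and a descriptive comparison with Zovirax" Cream. Sample size calculation sizes the trial on that comparison, giving the number needed "to show superiority of pritelivir compared with placebo with 80% power and assuming a type I error rate of 5"%, with 26% of placebo subjects and 50% of pritelivir subjects assumed to have non-ulcerative lesions. The result is 71 evaluable recurrences per arm.

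Primary efficacy analysis then names two sets: "The primary efficacy analysis will be performed in the ITT (Intend to Treat Set) and the PPS (Per-Protocol Set"). The ITT there is the randomized subjects with at least one application and at least one later lesion assessment. The other set is nested in it: "PPS is a subset of the ITT excluding subjects with major protocol violations". Secondary efficacy analyses uses the same pair: "The secondary efficacy analyses will be performed in the ITT and the PPS". Safety names a single set: "All safety analyses will be performed in the Safety Set".

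No section calls either efficacy set primary or supportive, requires significance in both, or says what follows if they differ.

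**The concern.** One hypothesis, one 5% error rate and one 80% power appear to be attached to two results. Taken literally, the sentence allows three rules: the ITT decides, a win in either set suffices, or both sets must win. Their operating characteristics differ. An either-set rule gives two chances at significance and raises the error rate. A both-sets rule lowers power below the planned figure. If no rule were fixed before unblinding and the sets fell on opposite sides of the threshold, the sponsor could pick the reading after seeing the data. Because the PPS excludes subjects after randomization, a claim resting on the PPS alone would be the weakest form of evidence for superiority.

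**Working it through.** **Inputs from Sample size calculation:** placebo 26%, pritelivir 50%, type I error 5%, power 80%, 71 per arm.

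**Assumptions not in the documents:** two-sided 5%; 71 per arm in the ITT; each ITT subject stays in the PPS with probability 0.95, 0.90 or 0.85, regardless of outcome; the same test in both sets.

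**Step 1. Reproduce 71 per arm.** The mean proportion is (0.26 + 0.50)/2 = 0.38 and the difference is 0.24.

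n = [1.960·√(2·0.38·0.62) + 0.842·√(0.26·0.74 + 0.50·0.50)]² / 0.24² = 63.0

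With continuity correction: n′ = (n/4)·[1 + √(1 + 4/(n·0.24))]² = 71.1

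The corrected two-sided calculation therefore gives the plan's 71. One-sided versions need 50 (uncorrected) or 58 (corrected), so they do not. Exact properties of a single test at 71 per arm:

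- corrected: power 79.8%, error 3.1% (26% in both arms);
- uncorrected: power 84.6%, error 5.2%.

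The planned figures are those of one test in one set of 71 per arm.

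**Step 2. How often would the sets disagree on significance?** Simulated trials at 26% versus 50%:

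| Excluded from PPS | 5% | 10% | 15% |
|---|---|---|---|
| Corrected: sets disagree | 5.4% | 8.5% | 11.5% |
| – ITT only significant | 3.6% | 6.5% | 9.4% |
| – PPS only significant | 1.8% | 2.0% | 2.1% |
| Uncorrected: sets disagree | 4.6% | 7.2% | 9.8% |
| – ITT only significant | 3.1% | 5.5% | 7.9% |
| – PPS only significant | 1.5% | 1.7% | 1.9% |

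The two estimates have opposite signs in under 0.2% of trials.

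**Step 3. What would each rule do (corrected test)?**

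- ITT decides: power 79.8%, error 3.1%, at any PPS size.
- Either set: power is 79.8% plus the PPS-only share, so 81.6/81.8/81.9%. Error simulated with 26% in both arms is 3.8/4.1/4.3%, still below 5%.
- Both sets: power is 79.8% minus the ITT-only share, so 76.2/73.3/70.4%. The error cannot exceed the ITT's own 3.1%.

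With the uncorrected test, the either-set rule gives an error of about 6.2 to 7.0%.

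**Step 4. Which of this would a label change?** The disagreement rates in Step 2 follow from comparing a sample with its own subset, and they stay the same whichever set is labelled primary. In the ITT-only cases the usual reading already gives the answer that a label would give. Only the PPS-only cases, about 2%, could tempt anyone into a claim that the ITT does not support.

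**The case for a change.** The strongest case is that word order is not a rule, that the two sets are joined on equal terms under the heading for the primary analysis, and that the document names one set where it wants one, as it does for safety. Superiority is to be tested formally even in phase 2, and a label would cost a sentence and no subjects. The document names no test, so the uncorrected either-set error of about 6.2 to 7.0% cannot be ruled out. A both-sets rule would cost 3.6 to 9.4 points of power with the corrected test. The calculation also takes exclusions as unrelated to outcome, which major protocol violations need not be.

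What stands: the wording does not rank the sets, and recording the ranking before unblinding is good practice. Outcome-related exclusions could change the figures, though they also give analysts a reason to let the ITT decide.

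What does not stand: the step from this silence to a choice made after the data are seen. The summary also gives no test, no sidedness, no missing-data rule and no list of major violations, so a missing label is weak evidence that the full plan lacks one. No section states an either-set or a both-sets rule, and the excess error and lost power arise only under those rules. The single safety set says nothing about how the two efficacy sets rank.

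**Conclusion.** The observation about the wording is correct, but it shows no error in the plan. It is a detail left out of an abridged document. Analysts would fill it in the ordinary way for a superiority trial: test pritelivir against placebo once in the ITT, and report the PPS alongside as support. On that reading the 5%, the 80% and the 71 per arm are all consistent.

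The residual exposure is a result significant in the PPS alone. That is about 2% of trials at the planning rates (1.8 to 2.1% corrected, 1.5 to 1.9% uncorrected), assuming 5 to 15% excluded unrelated to outcome, two-sided 5% and 71 per arm in the ITT. Both sets are to be analysed, so reporting both would show such a split. A label in the full plan would be tidy, but the point does not call for a change.

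### Does the primary comparison lose worthwhile power because the summary names no test and no adjustment for lesion stage at the first application?

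*Combined protocol and SAP*

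**What the plan says.** The document calls itself "Summary of the Clinical Trial Protocol and Statistical Plan". Under Trial design it states that "The statistical superiority will be tested against placebo", with Zovirax compared descriptively. Sample size calculation assumes non-ulcerative lesions in 26% of placebo and 50% of pritelivir subjects, 80% power and a 5% type I error, and arrives at 71 evaluable recurrences per arm. Primary efficacy analysis reads "The primary efficacy analysis will be performed in the ITT (Intend to Treat Set) and the PPS (Per-Protocol Set" and adds only the definitions of the two sets.

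Four further places bear on stage at the first application:
- **Trial design:** treatment is "initiated by the subject within one hour of noticing the first sign or symptom (eg, prodrome) of a recurrence of herpes labialis (HL".
- **Inclusion criteria, item 3:** "Subjects should have experienced prodromal symptoms in at least 50% of rHL episodes", and they "should have developed ulcerative lesions that have progressed through vesicle, ulcer, and crust stages in at least 50% of the episodes".
- **Inclusion criteria, item 10:** subjects with a current lesion "must not to treat the lesion present at randomization with the trial medication".
- **Subject diary documentation, item 4:** the subject notes lesion stage whenever trial treatment is applied. The text does not say whether the entry comes before or after the dose. Investigator staging (Efficacy measurements) begins only after the subject has started treatment.

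**The concern.** Two things make this look like a gap. First, a superiority test is announced and sized, yet the section on the primary analysis does not say which test it is. Secondly, subjects may start at any first sign, and no stage limit is set. A lesion that is already vesicular when treated has probably lost its chance of being non-ulcerative. The secondary endpoint "Maximum lesion area (length x width) for ulcerative lesions during the vesicular, ulcerative and hard crust stages" places vesicles in the course of ulcerative lesions, although the summary does not define non-ulcerative and the staging list keeps vesicle and ulcer apart. If late starts are common and almost never succeed, they add noise to both arms, and a test stratified by starting stage would remove some of it.

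At stake would be a few points of power, obtainable through analysis wording and one diary instruction. Validity is not in question.

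**Working it through.** **1. The plan's own figure.** Inputs from Sample size calculation: p1 = 0.26, p2 = 0.50, difference 0.24, mean 0.38, power 80%, alpha 5%. The summary does not state sidedness; two-sided reproduces its figure.

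Uncorrected: n = [1.96·√(2·0.38·0.62) + 0.8416·√(0.26·0.74 + 0.50·0.50)]² / 0.24² = (1.3454 + 0.5598)² / 0.0576 = 63.0 per arm.

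Continuity-corrected: n' = (63.0/4)·[1 + √(1 + 4/(63.0·0.24))]² = 71.1 per arm.

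The stated 71 matches the corrected formula (72 if rounded up). Exact enumeration at 71 per arm gives 79.8% power for Fisher or the corrected chi-square, and 84.6% for the uncorrected chi-square (actual size 5.18%). The trial is therefore adequately sized for any usual unadjusted test.

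**2. What stratifying could add.** The document supplies only 26%, 50% and 71 per arm. Everything else is assumed:
- a share v of 5, 10, 15 or 20% of lesions is vesicular or later at the first dose, with 10% success in both arms;
- of the other lesions, 70% start as prodrome/erythema and 30% as papule/edema;
- papule/edema succeeds either as often as prodrome/erythema or 0.6 times as often.

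Rates are scaled to keep 26% and 50% overall. For example, with v = 10% and factor 0.6, prodrome/erythema succeeds in (0.26 − 0.10·0.10)/(0.90·(0.7 + 0.3·0.6)) = 0.25/0.792 = 31.6% on placebo and 0.49/0.792 = 61.9% on pritelivir.

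The test is a three-stratum CMH without continuity correction, compared with the uncorrected chi-square at 84.6%. Power is simulated, with Monte Carlo error of about 0.1 point.

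| Stage recording | v = 5% | 10% | 15% | 20% |
|---|---|---|---|---|
| 10% misreported across the late boundary only; papule/edema equal | 84.3 | 84.7 | 85.1 | 85.7 |
| Same; papule/edema 0.6 times | 85.4 | 85.8 | 86.3 | 86.9 |
| Same, factor 0.6, plus 20% confusion between prodrome/erythema and papule/edema | 84.7 | 85.1 | 85.6 | 86.1 |

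The differences from 84.6% are −0.3/+0.1/+0.5/+1.1 points in the first row, +0.8/+1.2/+1.7/+2.3 in the second and +0.1/+0.5/+1.0/+1.5 in the third.

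The second row assumes that subjects never confuse the two early stages. Yet that is a distinction they must make themselves, on their own lip, and it is what produces the extra gain over the first row. Once 20% are confused, most of that extra gain is gone. At 30% the total gain is about 0 to 1.4 points across the same range of v. With no late starts and 20% confusion it is about nil or slightly negative. If stage carries no prognostic information, stratifying costs about 0.4 to 0.7 points.

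**3. Which column is likely.** The document gives no share of late starts. The one-hour rule, the required prodrome history and the bar on treating a lesion present at randomization all work against late starts. They point to the left-hand columns, where the third row gains 0.1 to 0.5 points.

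**4. Scale.** Exact uncorrected power rises from 84.6% at 71 per arm to 86.5% at 74, so even a gain of nearly 2 points is worth only three recurrences per arm. The plan randomizes 360/3 = 120 per arm and expects about 60% to be evaluable, which is 72. If the rate of no recurrence or dropout were 38% instead of 40%, that alone would add 120·0.02 = 2.4 per arm.

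**The case for a change.** The strongest case for a change has three parts.

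**The test should be named.** At 71 per arm, Fisher or a corrected test and the uncorrected chi-square differ by about 5 points of power (79.8% against 84.6%), more than stratifying is likely to add. It stands that this summary does not settle the choice. But a summary's silence says little about the full plan, and even the more conservative choice delivers the planned 80% almost exactly. The 5 points come from the continuity correction and are no argument for stratifying by stage.

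**Stage is a legitimate factor.** Subjects are randomized before the recurrence they treat, so starting stage cannot be a randomization stratum. If it is entered before the first dose in a double-blind trial, treatment cannot influence it, and the CMH test holds its level (simulated type I error 4.9 to 5.1%). That stands with its condition, and the diary section does not guarantee the condition. The entry is also self-reported, may be missing, and would need pooling and missing-data rules inside the primary test.

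**The gain could be larger.** With accurate recording and no success among late lesions, power reaches 85.5 to 91.1%. Under a different model, with a common odds ratio of 5 per stage step, four strata and perfect recording, the gain reaches 9.2 points. These figures are correct for their assumptions. That same model, with an odds ratio of 3 and an 85/15 split between two strata, gives +0.9 with perfect recording and 0.0 with 20% misrecording. With 20 to 40% misrecorded, odds ratios of 1 to 3 and two or three strata, it gives −0.5 to +1.6. The large gains need accuracy and prognostic strength that nothing in the document supports.

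**Conclusion.** The concern does not hold. Following the summary as written, with an ordinary unadjusted comparison of two proportions, gives a valid test at the planned power: 79.8% corrected, 84.6% uncorrected. Stratifying by diary stage would change power by about 0 to 0.5 points at 5 to 10% late starts, about 1.0 to 1.5 points at 15 to 20%, and nothing or a slight loss with none. These figures assume 10% misreporting across the late boundary, 20% confusion between the early stages, 10% success among late lesions and a 0.6 success ratio for papule/edema. None of these comes from the document, and better recording or stronger prognosis would raise the gain.

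Against that uncertain return, the change would put a self-reported item, recorded after randomization and of unstated timing relative to the dose, into the primary test. Statisticians may reasonably differ on that choice, and leaving it out is not a flaw. The unnamed test is a detail that a summary may omit.
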